2 STUDY SUMMARY

Title: A Phase II Trial of Inhaled Carbon Monoxide for the Treatment of Acute Respiratory Distress Syndrome (ARDS)

Objective: To evaluate the safety, tolerability, and efficacy of inhaled carbon monoxide (iCO), as well as to examine the biologic readouts of low dose iCO therapy in patients with ARDS.

Hypotheses:

- Low dose iCO will be safe and well-tolerated and will reduce mtDNA levels in ARDS patients.
- Low dose iCO will reduce the severity of lung injury and non-pulmonary organ failure in ARDS patients.
- Low dose iCO will reduce mitochondrial dysfunction, attenuate inflammasome activation, and promote resolution of inflammation in ARDS patients. Furthermore, we hypothesize that modulation of these pathways will predict improvements in the clinical outcomes of our Phase II trial.

Study Design:

1. Multi-center, prospective, randomized, partially double-blind, placebo-controlled Phase II clinical trial of inhaled CO for the treatment of ARDS.
2. 32 intubated, adult patients with ARDS will be randomized in a 1:1 ratio to receive either inhaled CO or inhaled air placebo for up to 90 minutes daily.
3. Subjects will be randomized to CO will be administered 200 ppm iCO to achieve a target COHb level of 5-8%.
4. Treatment will continue for 3 days, until discontinuation of mechanical ventilation, or death, whichever comes first.
5. Patients will be followed for 60 days or until discharge from the hospital to home with unassisted breathing, whichever occurs first.
6. Vital status and neurocognitive testing will be performed at 6 months via telephone interviews.

Sample Size/Interim Monitoring:

1. A total of 32 subjects will be enrolled.
2. The primary analysis will be safety and efficacy.
3. Trial progress will be monitored by an independent Data and Safety Monitoring Board (DSMB). The DSMB will monitor trial quality and feasibility approximately every 6 months and will be available as needed on *ad hoc* basis.

Study Population: All intubated patients ≥ 18 years old with ARDS according to the Berlin criteria will be eligible for inclusion. Subjects will be recruited from the medical, surgical, cardiac, and burn ICUs at each center with a *specific focus* on patients with ARDS secondary to infection, trauma, transfusion, burns, hemorrhagic shock,

inhalation, and/or oxygen exposure.

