1. Completion of the third dose of study drug

2. Discontinuation of mechanical ventilation
3. Death
4. Pre-specified criteria met for permanent discontinuation of study drug (**Section 7.1.8**)

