4.7 FOCUSED SAFETY ANALYSIS

The incidence of elevation in plasma COHb $\geq 10\%$ measured on study days 1-3 and pre-specified administration-associated adverse events (**Section 7.1.8**) and serious adverse events (**Section 9.7**).

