7.1.3 DOSING AND ADMINISTRATION

Subjects will be treated with inhaled CO at a dose of 200 ppm or placebo. Placebo will consist of medical-grade air in identical appearing aluminum AG gas cylinders.

The study drug will be administered for up to 90 minutes daily for three days following randomization or until discontinuation of mechanical ventilation, whichever occurs first. For patients who have a tracheostomy, the equivalent of extubation for the purposes of this protocol will be breathing via tracheostomy with unassisted breathing.

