7.1.4 CO MONITORING

The study drug concentration will be monitored continuously with the COventDS built-in analyzer to assure that the accurate dose is delivered. A physician investigator will assess subjects prior to daily iCO treatment. Subjects will have blood drawn daily for measurement of COHb and lactate prior to study drug administration. If COHb \geq 3% (assessed by unblinded physician) or lactate \geq 4 mmol/L, the study drug will be held and the subject will be reassessed for treatment the following day. An electrocardiogram (EKG) will also be performed daily prior to study drug administration to evaluate for cardiac exclusion criteria. Blood COHb levels will be measured with an IL GEM Premier Co-oximeter and SpCO measured with a noninvasive pulse oximeter (Masimo Radical-7).

Blood (arterial or venous) will also be drawn at 20, 60, 75, 90, and 180 minutes for safety monitoring of COHb levels. If an arterial line is not available, venous blood will be used for COHb monitoring as we⁴⁸ and others¹⁴³⁻¹⁴⁵ have shown that venous levels are as accurate and reliable as arterial measurements. Blood (arterial or venous) will also be drawn for blood gas analysis (using the local clinical lab) at 90 minutes or at the completion of treatment, if discontinued sooner than 90 minutes. If arterial blood is not available and venous blood gas is used, PaO₂/FiO₂ will be estimated using the formula $SpO_2/FiO_2 = 64 + 0.84 \times PaO_2/FiO_2$, as long as SpO₂ \leq 97% and subject remains intubated as described in the Statistical Analysis Plan.

The unblinded physician will review and adjudicate COHb measurements and communicate any study drug treatment holds to the administering study staff. COHb levels will be entered into the electronic case report forms (eCRFs) in a separate limited-access project in StudyTRAX by the unblinded RT or physician. The study drug will be administered for up to 90 minutes daily for up to 3 days following randomization or until discontinuation of mechanical ventilation, whichever occurs first.

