Note, troponin (I or T) may be increased in patients with sepsis and ARDS¹⁵⁰ in the absence of an acute MI or ACS from coronary artery disease. If, in the judgment of the clinical team, an ARDS patient with elevated troponin levels has no other indication of an MI or ACS, the patient may still be eligible for enrollment.

In addition, if a subject develops the following criteria during the study, the study drug will be held until resolved:

- Severe hypoxemia defined as $\text{SpO}_2 < 95$ or $\text{PaO}_2 < 90$ on $\text{FiO}_2 \geq 0.9$
- Hemoglobin < 7.0 g/dL
- Diffuse alveolar hemorrhage from vasculitis
- Use of high frequency ventilation
- Use of inhaled pulmonary vasodilator therapy (eg. NO or prostaglandins)
- Use of ECMO

If study drug hold criteria are met, the study drug will be held and subjects will be evaluated on a daily basis and assessed for whether a given criteria has resolved and whether study drug treatment may be resumed.

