7.1.9 COMPLETION OF THE STUDY DRUG ADMINISTRATION

Subjects will be considered to have completed the study drug administration portion of the study when one of the following conditions is met, whichever comes first:

1. Three days after study drug administration
2. Discontinuation of mechanical ventilation
3. Death

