9.1.1 STUDY SAMPLE COLLECTION

Sample collection will be done according to the **Time-Events Schedule** in **Section 1.3**.

COHb Levels: COHb levels will be measured using the IL GEM Premier Co-oximeter at specified time points on Days 1 through 3. See **Section 9.5.2**.

Plasma Samples: Blood (4 mL on days 1-3) will be collected pre-treatment in EDTA anti-coagulated tubes for plasma isolation and measurement of biomarkers of mitochondrial dysfunction, inflammasome activation, lipid mediators, and cytokines. Blood will be collected (4 mL on days 1-3) post-treatment (at 90 min and 3 hrs). Blood (4 mL) will also be collected for plasma isolation on Day 5. Plasma will be obtained and divided immediately after centrifugation into equal aliquots in specified tubes and frozen at -80°C .

RNA Samples: On days 1-3, blood (2.5 mL) will be collected in Paxgene tubes for RNA isolation. Blood will be collected in Paxgene tubes before and after (at 90 min and 3 hrs) study drug administration, and frozen at -80°C . Blood (2.5 mL) will also be collected in Paxgene tubes for RNA isolation on Day 5, and frozen at -80°C .

DNA Samples: Cell pellets will be obtained for future DNA isolation from the blood collected in EDTA tubes on days 1-3 and on day 5. Cell pellets will be isolated pre-treatment and post-treatment (at 90 min and 3 hrs) on days 1 through 3. On days 1 and 5, the 8 mL tube may be used to isolate cell pellets if unable to obtain an adequate pellet from the 4 mL tube on that day.

Primary Cell Isolation: An additional 8 mL of blood will be drawn for isolation of peripheral blood mononuclear cells (PBMCs) pre-treatment on day 1 and post-treatment on day 3.

Urine Sample Collection: Between 50-100 mL of urine will be collected in a sterile specimen container on days 1-3 and on Day 5. Cell pellets will be isolated pre-treatment and post-treatment (at 90 min and 3 hours) to obtain RNA and protein, as well as mtDNA.

Discarded Specimens: Discarded bronchoalveolar lavage (BAL) fluid and plasma will be obtained (when available) for levels of cytokines, mediators/biomarkers, and protein. Plasma and BAL fluid will be divided into equal aliquots in specified tubes and frozen at -80°C .

A total of approximately 88.5 mL of blood will be collected for research samples during the study from each study subject as follows:

Sample collection	Day 1	Day 2	Day 3	Day 5	Total Volume
ABG, lactate, and COHb analysis	2.5 mL	2.5 mL	2.5 mL		7.5 mL

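### The end of treatment is a dose count in one place and a three-day period elsewhere, and no section says whether a held dose is made up

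*Combined protocol and SAP*

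**What the plan says.** **Completion rules**

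- Section 2, stop list: treatment ends at "Completion of the third dose of study drug", or at the end of ventilation, death or permanent discontinuation. There is no calendar limit.
- Section 2, study design item 4: "Treatment will continue for 3 days, until discontinuation of mechanical ventilation, or death, whichever comes first".
- Section 7.1.3: "The study drug will be administered for up to 90 minutes daily for three days following randomization". Sections 7.1.4 and 9.5.2 use nearly the same words ("for up to 90 minutes daily for up to 3 days following randomization").
- Sections 5.3 and 7.1.5 speak of consecutive days, and the schedule in 1.3 marks CO administration on Days 1 to 3 only.
- Section 7.1.9: "Three days after study drug administration". It has no dose count and does not name the administration from which the days run.

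**Holds**

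- Section 7.1.6 lists ten hold criteria, four and then six. For the six it says that "if a subject develops the following criteria during the study, the study drug will be held until resolved". For COHb and lactate, the drug waits for the next day's scheduled dose and the values are measured again.
- Section 8.1 has held patients reviewed daily for resumption.
- Section 7.1.8 stops drug permanently after three missed doses because of raised baseline COHb or adverse events.

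**What depends on dosing days**

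- The primary efficacy endpoint (4.4) is the change in mtDNA to day 5.
- Section 10.4.3 allows secondary and exploratory analyses by number of doses completed.
- Section 4.7 counts COHb of 10% or more "measured on study days 1-3 and pre-specified administration-associated adverse events", and 9.1.1 places COHb measurement "at specified time points on Days 1 through 3".

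**The concern.** A dose-count rule and a calendar rule agree when no day is held. After a hold they can part: one keeps the patient on drug until a third dose is given, the other lets the missed dose go. Two sites following different sections could treat identical patients differently.

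Two quantities used in the analysis would then depend on the section read: the number of doses, and the interval from last dose to the Day 5 mtDNA sample. With 32 patients at seven sites, a few discordant cases are a visible share of the data. The Day 1–3 windows in the schedule, 4.7 and 9.1.1 also fit only one of the rules.

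**Working it through.** The plan gives no figure for this point, so there is nothing to reproduce. The check counts doses under each reading and then bounds how many patients could be affected.

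**1. Readings.** Assume one dose per day, first scheduled dose on Day 1 as in 1.3, and a patient who can be dosed on every day not held while ventilated. Let f be the day of the first dose actually given.

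- A (section 2 stop list): unheld days counted until three doses are given.
- B (three days after randomization, as in 1.3, 7.1.3, 7.1.4 and 9.5.2): unheld days among Days 1 to 3.
- C (7.1.9 as a three-day window from first dose): unheld days from f to f+2.
- D (7.1.9 as running through the third day after first dose): unheld days from f to f+3.

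**2. Doses for a patient ventilated and dosable through Day 7**

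| Days held | A (day of third dose) | B | C | D |
|---|---|---|---|---|
| none | 3 (Day 3) | 3 | 3 | 4 |
| 1 | 3 (Day 4) | 2 | 3 | 4 |
| 2 | 3 (Day 4) | 2 | 2 | 3 |
| 3 | 3 (Day 4) | 2 | 2 | 3 |
| 1 and 2 | 3 (Day 5) | 1 | 3 | 4 |
| 1 and 3 | 3 (Day 5) | 1 | 2 | 3 |
| 2 and 3 | 3 (Day 5) | 1 | 1 | 2 |

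The main comparison is A against B: 3 versus 2 after one hold, 3 versus 1 after two. C and D show that 7.1.9 does not settle the count. C matches A when only Day 1 is held and matches B when only Day 2 or 3 is held. D would allow a fourth dose with no hold, which the three-day wording elsewhere excludes, so nothing below rests on it.

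**3. When A and B agree.** If ventilation ends by Day 3, A and B give the same count for every hold pattern (Day 2 held: 2 and 2). If it ends on Day 4, one hold gives 3 versus 2 and two holds give 2 versus 1.

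**4. Gap to the Day 5 sample** (5 minus day of last dose, patient dosable as needed)

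- No hold: 5 − 3 = 2 days under both.
- One hold: A gives 5 − 4 = 1 day. B gives 5 − 3 = 2 days if Day 1 or 2 was held, and 5 − 2 = 3 days if Day 3 was held.
- Two holds: A gives 5 − 5 = 0 days. B gives 2, 3 or 4 days, as the single dose fell on Day 3, 2 or 1.

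At a gap of zero the order of dose and sample is undefined, because 9.1.1 sets pre- and post-treatment plasma timing only for Days 1 to 3.

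**5. Chance of any hold.** The hold rate h per patient-day is not in the documents, so it is assumed, with independent days: P(at least one hold in 3 days) = 1 − (1 − h)³.

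- h = 0.05: 1 − 0.95³ = 0.143
- h = 0.10: 1 − 0.90³ = 0.271
- h = 0.20: 1 − 0.80³ = 0.488

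Of 32 patients these are 0.143 × 32 = 4.6, 0.271 × 32 = 8.7 and 0.488 × 32 = 15.6.

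**6. The three-missed-dose rule in 7.1.8.** Under B, three missed doses use all three days, leaving 3 − 3 = 0 doses given. Only a patient who was never dosed could meet that rule.

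**The case against.** The strongest reply is that the three-day wording dominates. It stands in the synopsis, section 2 itself, 5.1, 5.3, 7.1.3 to 7.1.5, 9.5.2 and the schedule, and 7.1.8, 7.5 and 8.1 refer to a three-day treatment period. The stop-list line could then mean at most three doses within those days. The wording for COHb and lactate holds, and the term missed doses in 7.1.8, also suit doses that are lost rather than deferred. This is a fair reading, but no section states it. The stop list sets no calendar limit, and 7.1.6 and 8.1 let treatment resume once a criterion resolves.

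A second reply is that dose number and timing already vary through extubation, holds and discontinuation. That is true and limits the harm. Variation from the patient's course is part of the design, however; variation from which section a site reads is not.

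Three stronger readings are tempting and are not supported.

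- **Every patient with a held day is affected.** Step 3 shows otherwise: the patient must still be ventilated, dosable and not permanently discontinued after Day 3.
- **COHb of 10% or more after a Day 4 dose would be lost to the safety analysis.** It would miss only the Day 1–3 limb of 4.7. Sections 7.1.8 and 9.7.4 list it as an administration-related event with no day limit, 4.7 counts those events in its second limb, and it is also in the primary safety endpoint (4.3), where reporting runs through study day 7.
- **A Day 4 dose would go unmonitored.** Sections 7.1.4 and 7.1.7 tie COHb draws to each treatment, and footnote G of the schedule refers to days of administration.

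**Conclusion.** The completion rule is internally inconsistent: a dose-count rule without a calendar limit and a three-day rule cannot both be followed after every hold, and 7.1.9 leaves its starting point open. For the patients described, the rules differ by one dose after one hold and by up to two after two, and the last dose under the third-dose rule falls closer to the primary endpoint sample.

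The 14%, 27% and 49% are upper bounds on the share for whom the third-dose and Day 1–3 rules differ, not estimates of it. They rest on assumed daily rates and independent days. Holds that persist from day to day would, at the same daily rate, make any hold less likely, and some held patients will be extubated, die or be discontinued before the rules diverge.

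On safety, the finding is limited to misaligned Day 1–3 windows in the schedule, 4.7 and 9.1.1. This should be corrected because it touches doses given and primary endpoint timing, and correction is cheap.

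**What to change.** Reconcile section 2 (design item 4 and the stop list) and sections 5.3, 7.1.3, 7.1.4, 7.1.5, 7.1.8, 7.1.9 and 9.5.2 to one completion rule. The rule should state:

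- the event that starts the clock;
- whether a held dose is made up.

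Which rule applies is the sponsor's clinical decision, and no view is offered here. Once it is chosen, align the schedule in 1.3, the sampling days in 9.1.1 and the COHb window in 4.7 with every day on which a dose can be given. If a dose can fall on Day 5, state its order relative to the mtDNA sample.

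The cost is wording in a protocol amendment and notice to the sites. No extra patients are needed.

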7.1.10 TREATMENT IN COVID-19 SUBJECTS

For enrolled ARDS patients with COVID-19 infection, all research and clinical staff will conform to each site's hospital infection control guidelines for COVID-19 positive patients with appropriate personal protective equipment (PPE) for enhanced respiratory isolation precautions. All research and clinical staff will have appropriate training on PPE, be fit-tested, and wear an N95 respirator or powered air-purifying respirator (PAPR) if staff cannot be fit-tested, face shield or other eye protection, gloves, and gown when entering the subject's room for treatment or sample collection. Gown, gloves, and eye protection will be doffed upon exiting the subject's room either just inside or just outside the door, and hand hygiene will be performed. Respiratory protection should be removed after exiting the subject's room unless extended use is being practiced.

During study treatment, all staff will conform to each site's hospital infection control guidelines regarding treatment of COVID-19 positive mechanically ventilated patients with inhaled therapies. Staff will be limited to essential personnel in the room. All equipment will be single-use or dedicated to use of the subject to avoid sharing with other subjects. Reusable equipment will be disinfected with a hospital-approved disinfectant before use in another subject.

Blood sample collection and handling will be performed according to each site's hospital infection control guidelines for COVID-19. Samples obtained from a subject will be put in a tube by research or clinical staff, and the tube will be wiped down with a hospital-approved disinfectant. While holding the tube with the wipe, the specimen tube will be carefully placed into a clean specimen bag held by a monitor or nurse outside the room. The specimen bag will in turn be wiped down with a hospital-approved disinfectant. A member of the research team will pick up the research specimens and transport them to a BSL2+ laboratory in a secondary container. Research samples will only be processed in hospital biosafety committee approved BSL2+ laboratory facilities.

7.2 PREPARATION/HANDLING/STORAGE/ACCOUNTABILITY

7.2.1 ACQUISITION AND ACCOUNTABILITY

Each participating site is responsible for the ordering, storing and dispensing of the investigational agent(s). Each study team will keep a record of CO/placebo tanks received, administered, and returned at the study site in a Site Drug Accountability Log. This log will include Lot #, date and amount/concentration received, subject ID, date and time administered, date and time administration ended, date and amount/concentration returned.

7.2.2 FORMULATION, APPEARANCE, PACKAGING, AND LABELING

The study drug will be provided for this study by Praxair Healthcare Services (Morrisville, PA). Gas mixtures will be manufactured with United States Pharmacopeia (USP)/Ultra High Purity (UHP)/National Formulary (NF) components. The mixtures will be prepared as a Certified Standard with a blend tolerance of $\pm 10\%$ and analytical uncertainty of 2%.

The gas mixture provided to subjects randomized to CO will be 5000 ppm CO (balance air) and will be provided to study sites by Praxair Healthcare Services (Morrisville, PA) in AG aluminum cylinders with a CGA 500 valve. The gas cylinder's nominal size is 5 inches in diameter by 17 inches tall, contains 360 liters of 5000 ppm (0.5%) CO in room air (21% oxygen), and poses no increased flammability risk. The 5000 ppm CO source gas will be administered via the CO Delivery System (12th Man Technologies, Garden Grove, CA) and delivered to subjects at a dose of 200 ppm.

The mixture components include: **Carbon Monoxide UHP Grade 3.0** (Assay 99.9%; O₂ <10 ppm, H₂O <5 ppm, N₂ <900 ppm and CO₂ <20 ppm); and **Medical Air USP**. The source materials for **Medical Air USP** include: **Oxygen USP** (Assay ≥ 99.2%; Odor- none; Oxygen produced by air liquefaction process, does not require CO and CO₂ analysis); and **Nitrogen NF USP** (Assay ≥ 99.2%; Identification- OK, Paramagnetic Assay Method; CO ≤ 10 ppm; Odor- none).

The gas mixture provided to subjects randomized to placebo will be medical grade air and will be provided to study sites by Praxair Healthcare Services (Corona, CA) in AG aluminum cylinders with a CGA 346 valve. With the exception of the 346 valve, the placebo gas cylinders will be identical in size and color as the CO cylinders. The placebo gas will be administered via the CO Delivery System (12th Man Technologies, Garden Grove, CA) and delivered to subjects in an identical fashion as the CO gas.

7.2.3 PRODUCT STORAGE AND STABILITY

The CO and placebo air cylinders will be stored at room temperature in a secure area at each center. The cylinders will be stored and handled according to each site's Compressed Gas Cylinder Storage Guidelines. The CO and placebo air cylinders will be returned to Praxair upon expiration. The expiration date is generally three years from the date of fill and is clearly indicated on the certificate of analysis for each cylinder.

7.2.4 PREPARATION

As described in the SOP, the CO Delivery System will be calibrated and performance testing conducted daily prior to use. The calibration will be performed as described in the Operator's Manual in **Appendix A**. The calibration consists of a low (21%) and high (100%) range O₂ calibration, followed by a low (100 ppm) and high (400 ppm) range CO calibration. After completion of the calibration, performance testing will be performed as described in the SOP. The CO Delivery System will be assembled, the appropriate gas cylinder (CO or air) connected, and the delivery system will be connected to the ventilator as described in **Appendix A**. As shown in **Figure 7**, the injector module will be connected between the inspiration port of the ventilator and inlet port of the humidifier. The gas sampling line will be placed between the outlet port of the humidifier and the patient wye as shown.

